## **Background and Introduction**

Heart disease is the leading cause of death in the U.S. Detection and characterization of coronary artery disease (CAD) can contribute significantly towards reducing mortality and improving quality of life for large numbers of people. Currently, SPECT and echo imaging are the clinical standards for non-invasive assessment of regional blood flows (perfusion) in the myocardium, but do not provide quantitative estimates of regional myocardial blood flow. While quantitative MRI perfusion, in its current state, is a useful clinical and research tool, improved methods are needed along with better benchmarks of how well the methods quantify perfusion in humans. The techniques proposed here will be advantageous for quantifying myocardial perfusion and are ideally suited for studying patients with atrial fibrillation.

Our initial cardiac MRI work under IRB 8157 and IRB 10342 has shown promising results and this project builds on these past experiences.

This protocol is to support the development and validation of new pulse sequences and automated mathematical modeling approaches to provide practical and accurate methods for assessment of myocardial perfusion and viability.

# **Purpose and Objectives**

This work seeks to develop, evaluate and use new MRI methods for non-invasive quantitative assessment of myocardial perfusion reserve (MPR). The methods will be designed to work robustly for patients with arrhythmias or poor ECG signals. The methods will be applied along with left ventricular (LV) and left atrial (LA) function and LA fibrosis measurements to study changes due to treatment for atrial fibrillation (AF).

Specific aims are (1) To design and test highly-undersampled ungated perfusion acquisitions and reconstructions. (2) To provide robust quantitative perfusion estimates by improved processing and by identifying an accurate arterial input function using methods that are widely applicable across a range of doses and acquisition types. (3) To determine the validity and repeatability of the proposed quantitative methods and the differences in perfusion and MPR measured at systole and diastole, including determining if systole or diastole is most repeatable when quantifying perfusion. (4) To determine the changes over time in perfusion reserve and cardiac function and left atrial fibrosis, after ablative treatment for AF. This will allow for determining the extent of perfusion improvement acutely due to conversion to sinus rhythm and the degree of recovery of perfusion reserve that recovers more slowly over months.

**pdf**element

The Trial Version

Population

ticipants: 18-60 +

Protocol Summary (ERICA) Page **2** of **7**  IRB\_00058133 IRB Approval 6/11/2019

#### Sample Size:

At Utah:	140
All Centers:	NA

#### Inclusion Criteria:

All participants will be over the age of 18 and able to provide consent

Control Group A (healthy or non-AF volunteers): Volunteers will be in normal sinus rhythm and available for at least one study visit.

Control Group B (risk based volunteers): Volunteers will consist of both normal sinus rhythm and suspected or confirmed paroxysmal or persistent AF.

Atrial Fibrillation MRI and PET cohort will have suspected or confirmed paroxysmal or persistent AF.

Atrial Fibrillation Blood Flow MRI cohort will be patients with paroxysmal or persistent AF that are scheduled for RF catheter ablation treatment. These subjects will require clinical MRI scans to assess pulmonary vein stenosis and LA fibrosis before ablation, 1-3 days after, and 6 months after ablation. The study visits will be schedule according to the three clinical MRIs. Research scans will not be added in the acute (1-3 days after) MRI studies, but at pre-ablation and at later time points.

#### **Exclusion Criteria:**

Exclusion criteria for all cohorts:

Critically ill patients, patients on ventilators, patients with unstable angina or with hypotension, asthmatics, and other patients whose medical care or safety may be at risk from undergoing an MRI examination will be excluded. Patients with claustrophobia will also be excluded from the study if this cannot be controlled with standard methods (valium or benadryl). Patients with contraindication to MRI (pacemaker, metal implants, or certain types of heart valves), pregnant patients, minors, mentally disabled patients and prisoners will be excluded from this study. (All criteria apply to patients and normal volunteers). Gadolinium nephrotoxicity will be addressed by having patients with abnormal kidney function (GFR<30) excluded from the study due to the (very small) risk associated with gadolinium contrast agents. This threshold may be modified, depending on practices determined by the Radiology Department and the IRB. Patients with a known allergy or contraindication to Adenosine and/or Regadenoson will be excluded from stress MRI cohorts.

All participants that will receive a stress agent will refrain from consuming caffeine for at least 12 hours prior to each MRI

tion cohorts:

**pdfelement** 

nts will be selected to have very low pre-test likelihood of coronary artery disease based on being c and having none of the following risk factors: diabetes, family history of premature coronary artery erlipidemia, hypertension, and smoking.

Protocol Summary (ERICA) Page **3** of **7**  IRB\_00058133 IRB Approval 6/11/2019 Volunteers:

No contra-indications in addition to those listed above for all cohorts. Volunteers with a known allergy or contraindication to Adenosine and/or Regadenoson will only be enrolled in scans where no stress agent will be administered.

## Design

Prospective Clinical Research

# **Study Procedures**

## **Recruitment/Participant Identification Process:**

Subjects will be recruited from those being treated by colleagues in the Cardiology clinic, that fit the inclusion criteria given above.

We are planning on using clinical schedule review and an opt in recruitment letter for increasing enrollment. We plan on being able to identify potential subject from the information gained from EPIC to meet subjects in the clinic. We will plan on discussing their possibility of being part of the research study with the physician prior to meeting the patient.

Healthy volunteers will be recruited by study coordinators and use of a volunteer information sheet (attached). A participant pool will be used to recruit healthy volunteers. This pool consists of previous study participants that have agreed to be contacted for future research studies.

Volunteers will also be recruited from the University of Utah using flyers (attached) posted on campus.

Participants who are University Staff, Students, and Faculty will be recruited only when there is not the chance of coercion or undue influence to participate in the study. Specifically, anyone who works for the PI or receives a grade from the PI will not be allowed to volunteer.

The volunteer information sheet will be given to people that contact the study staff and show interest in research participation.

The study will be listed online at http://healthcare.utah.edu/clinicaltrials with staff contact information listed for volunteers that would like to participate. We will also list the study in the ResearchMatch database (also known as the National Recruitment Registry Project).

**pdf**element

The Trial Version

Protocol Summary (ERICA) Page 4 of 7

### Description of location(s) where consent will be obtained:

At the hospital or at INC or at HCH, depending on which imaging study is being performed.

#### Description of the consent process(es), including the timing of consent:

When possible, consents are emailed to the participants a week ahead. Otherwise, consents are done prior to the imaging procedure when the subjects arrive at the imaging center. Subjects may take as much time as they like to read and ask questions, and to think about whether they want to participate.

#### **Procedures:**

STUDY PROCEDURE

As described in the participant characteristics, all subjects will be imaged with MRI, and some also with PET. All subjects enrolled in the AF cohorts will have three study visits or will consist of extra scans added to a clinically scheduled MRI. All subjects enrolled in the healthy volunteer and risk based cohorts will have at least one study MRI and up to three study MRIs depending on the study aim. It will not be a deviation if not all three visits are completed for these cohorts

For the below, LV=left ventricle, LA=left atrium, LGE=late gadolinium enhancement (to see atrial fibrosis), MRA=magnetic resonance angiography

MRI Protocol Each study will first hook up ECG and IV. Then the imaging protocol will include: 1) 0.05 mmol/kg adenosine or regadenoson stress perfusion, with initial 1/10 concentration volume matched dual bolus. For all perfusion sequences, gadolinium is given i.v. with a power injector at 5cc/s, 25 ml saline flush at 5cc/s. 2) LV cine with tags in the same 5 slices imaged with perfusion. 3) LV wall motion cine (without tags), short axis of whole heart. 4) 0.05 mmol/kg rest perfusion, with dual bolus. 5) MRA of the LA (used for guiding the ablation procedure) with 0.1mmol/kg. 6) Finish LV cines and do LA cines - 4 chamber view stack for LA function. 7) High resolution 3D LGE scan of the LA.

We estimate the time in the scanner (after IVs and ECG leads are in place) as 5 min. scouts, 10 min. perfusions, 5 min. MRA, 20 min. tags and cines, 10 min. LGE =  $\sim$ 60 minutes.

For the subjects undergoing repeated MRIs, a second MRI study will also be scheduled up to 10 weeks later to see how repeatable the MRI measurements are. The second MRI study will be identical to the first. A third MRI visit will be optional and offered to the subject at the end of the second MRI.

For the PET or PET/CT scans: a study at rest and at adenosine or regadenoson stress will be performed. For each PET study, you will receive through the IV a small amount of a radioactive tracer. Each scan will last approximately 30 minutes. A transmission scan or a low-dose X-ray CT scan to provide information about your anatomy in order to enhance the PET data will also be performed. (The PET data shows blood flow rather than body structure). This will take approximately 1-15 minutes.

For the subjects undergoing both an MRI and a PET scan, the order of the tests will depend on scheduling issues and may be on the same or different days. For both imaging sessions, you will be asked to not have any caffeine for at least 12 hours before the scan. An IV (Intra-Venous) line will be inserted into a vein in each of your arms, and ECG (electrocardiogram) leads will be placed on your chest or back.

A blood draw has been added to each cohort and for each study visit. A hematocrit will be ordered for the day of the study visit and will be drawn at the time the IV is placed in an attempt to limit patient discomfort. In the event that the lab can not be obtained while the IV is placed the patient will be escorted to the outpatient lab in the hospital after the scan has been

pdf element	•			
The Trial Version		Study Visit 1	Study Visit 2	Study Visit 3

	Day 1		
Control Group A Non-AF	MRI with contrast Blood Draw	*Optional Scan* MRI with contrast Blood Draw	*Optional Scan* MRI with contrast Blood Draw
	Day 1 within 10 weeks of 1st MRI		within 10 weeks of 2nd MRI
Control Group B with and without AF	MRI with contrast, stress agent and Blood Draw Agent and Blood Draw		*Optional Scan* MRI with contrast, stress agent and Blood Draw
	Day 1 PET or PET/CT can be c	within 10 weeks of first MRI	
MRI and PET Group AF	MRI with contrast and stress agent Blood Draw PET or PET/CT with radioactive tracer, stress agent and Blood Draw		MRI with contrast and stress agent Blood Draw
	Day 1 pre-ablation post ablation		final
Blood Flow MRI AF Clinical Scans	Clinical MRI with research scans, contrast, stress agent, blood draw	Clinical MRI with research scans, contrast, stress agent, blood draw	Clinical MRI with research scans, contrast, stress agent, blood draw

### Procedures performed for research purposes only:

All of the procedures described in #6, above, will be done for research purposes only, exce for the subjects that are undergoing clinical MRIs before and after AF ablation treatment (blood flow MRI AF clinical scans). In those subjects, some of the above scans will be performed and billed clinically. That is, the LV wall motion cines, the MRA, and the LGE the LA form a portion of the standard clinical scan.

# I Methods, Data Analysis and Interpretation

**pdfelement** 

lysis The primary hypothesis is that MPR will significantly increase due to ablation therapy. The omputed with a t-test) of any changes in perfusion and MPR will take into account the inter-study 1 D.3 by using the procedure by Bland-Altman. Considering 3 independent territories per study, and an MPR changes of 0.3, the power of a paired t-test to detect significant change is 85% with 20

Protocol Summary (ERICA) Page **6** of **7**  IRB\_00058133 IRB Approval 6/11/2019 patients. 30 subjects are planned and it is expected that ~33% of the patients will recur, leaving 20 subjects. Additional analysis of changes in MPR in the patients that recur will also be done, although with reduced power. Results from the gender and age-matched control group of 10 subjects without AF will be used to determine how MPRs before and after ablation compare to normal values.

Further comparisons of perfusion, MPR, function including strain, and LA fibrosis size will be done with t-tests and Bland-Altman methods. ANOVAs will be performed to analyze relations between MPR, function, and fibrosis size. MPR for coronary artery territories as well as smaller regions and division of each region into an endocardium portion and an epicardium portion will be studied with separate analyses. We do not expect MPR to be the best predictor of recurrence, since LA size and function and fibrosis are known to be powerful predictors. We will test if MPR is an independent predictor of recurrence. And a combined best linear predictor for recurrence will be constructed from the LA and LV function and size, along with LA fibrosis and perfusion values. This analysis will add to our understanding and serve as a basis for designing larger trials if there are particularly promising integrated metrics that predict response to therapy.

The longitudinal dataset that will be collected here will be extremely valuable. While the most unique piece with the most unanswered questions is the perfusion data, the inclusion of LA fibrosis which is still relatively new, along with LA and LV function and sizes forms a valuable resource that will be freely shared with the scientific community to allow additional analyses and comparisons. For example the results may shed light on whether MPR changes instigate the remodeling process, or result from the anatomical changes (smaller LA and improved function). If LA first shrinks and then MPR returns to baseline, this implies the latter.

The addition of obtaining labs from each subject at each visit will be to collect a hematocrit level for the day of the scan. The hematocrit can be used along with the T1 maps to calculate extracellular volume (ECV). We want to measure ECV along with perfusion and other parameters within this project.

The Trial Version

Protocol Summary (ERICA) Page **7** of **7**

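### The 85% power assumes three independent territories per patient; if it combines them, 20 patients do not deliver 85% at a valid 5% error rate once the territories are positively correlated

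*Combined protocol and SAP*

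**What the plan says.** The Methods, Data Analysis and Interpretation section takes an increase in MPR after ablation as the primary hypothesis and sizes the study on it. The calculation opens with "Considering 3 independent territories per study", takes an MPR change of 0.3, and states that "the power of a paired t-test to detect significant change is 85% with 20" patients. Enrolment follows from that 20: "30 subjects are planned and it is expected that ~33% of the patients will recur, leaving 20 subjects".

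Under Procedures, the MRI protocol for each study has one stress acquisition ("0.05 mmol/kg adenosine or regadenoson stress perfusion") and one rest acquisition ("0.05 mmol/kg rest perfusion, with dual bolus"). All territory MPRs in a study come from this pair. Under Inclusion Criteria, the ablation cohort is "patients with paroxysmal or persistent AF that are scheduled for RF catheter ablation treatment".

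Part of the statistics paragraph is lost in the text available for review. The SD of the change, alpha and sidedness cannot be read, so they are not treated here as missing from the plan. What can be read states no correlation between territories. It also does not say whether the primary test pools the territories, averages them per patient, or tests each one.

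**The concern.** Independence is written into the power calculation as an input. There are two reasons to expect the changes in one patient's territories to move together.

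- **Shared measurement.** An error in the stress or the rest acquisition enters all three MPRs of that study, and so all three changes. This reason is sufficient by itself.
- **Differences between patients.** If some patients gain more than others, their territories gain together. The cohort mixes paroxysmal and persistent AF, so such differences are plausible, although the documents do not quantify them. A mean effect common to all patients would not by itself create correlation.

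The harm depends on how the primary test is run. If it pools 60 territory differences, the main harm is false positives on the primary hypothesis. If it uses patient means, the main harm is lost power, and a null result could be misread as no effect of ablation. The section also says the results will inform the design of larger trials, so the error could carry forward.

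**Working it through.** **Inputs from the Methods section:** change 0.3; paired t-test; 85% power; 20 patients; 3 territories per study, so 20 × 3 = 60 differences if combined.

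**Assumed:** two-sided alpha 0.05; the same SD σ of the change in each territory; the same correlation ρ between any two territories of a patient. The values ρ = 0, 0.2, 0.5 and 0.8 are illustrative.

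**1. The plan's own figure.** The 85% cannot be reproduced, because SD and alpha are unreadable. It can be inverted. With n = 60 independent differences and noncentrality d√n on 59 df, 85% power needs d = 0.3933. If 0.3 is the mean change, σ = 0.3 / 0.3933 = 0.763. The recurrence arithmetic is consistent: 30 × 0.67 = 20.1.

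**2. Patient as the unit.** The variance of a patient's mean change is σ²(1 + 2ρ)/3. The standardised effect is therefore d√(3/(1 + 2ρ)), tested with n = 20 on 19 df. The change detectable with 85% power is 0.7065 × σ√((1 + 2ρ)/3), where 0.7065 is the effect giving 85% at n = 20.

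| ρ | Effect on patient mean | Power | Detectable change |
|---|---|---|---|
| 0 | 0.681 | 82% | 0.31 |
| 0.2 | 0.576 | 69% | 0.37 |
| 0.5 | 0.482 | 53% | 0.44 |
| 0.8 | 0.422 | 43% | 0.50 |

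The step from 85% to 82% at ρ = 0 is only degrees of freedom; the rest is correlation. With one-sided alpha 0.05, and the effect back-solved again, the powers are 83 / 71 / 58 / 49%.

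**3. Pooled t-test on 60 differences.** The true standard error of the mean is about √(1 + 2ρ) times the one the test uses: 1.18, 1.41 and 1.61 at ρ = 0.2, 0.5 and 0.8. By normal approximation the type I error is 2{1 − Φ(1.96/√(1 + 2ρ))}, or about 10, 17 and 22%. Simulation (200,000 data sets per setting, 20 patients × 3 territories) allows for the estimated SD:

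| ρ | Type I error | Rejection rate at the assumed effect | Power with type I error held at 5% |
|---|---|---|---|
| 0 | 5.0% | 85% | 85% |
| 0.2 | 9.7% | 81% | 72% |
| 0.5 | 16.8% | 77% | 56% |
| 0.8 | 23.3% | 75% | 45% |

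The pooled test appears to keep most of its power only because its error rate is no longer 5%.

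**4. If the 85% was computed on 20 patient means assuming independence.** The effect 0.7065 is divided by √(1 + 2ρ), giving 0.597 / 0.500 / 0.438 and power 72 / 56 / 46% at ρ = 0.2 / 0.5 / 0.8. Power falls below 80% once ρ exceeds about 0.07.

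**5. If each territory is tested separately.** With n = 20, 85% needs d = 0.7065, so σ = 0.3 / 0.7065 = 0.425. The correlation does not enter, and each test has 85% power at every ρ.

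**The case against.** The strongest reply is that the unit of the primary test cannot be read. If three separate territory tests were meant, step 5 applies and correlation costs no per-test power. The section does announce separate analyses by coronary territory. That sentence stands among the further comparisons, however, and on this reading independence would play no part in the power. Its appearance as an input favours combining without proving it. The loss is therefore conditional, and that part of the reply stands.

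The lost text also lies close by. A damaged sentence says inter-study variability will be handled with a Bland-Altman procedure. Nothing readable shows that this covers correlation between territories within a patient, but only the intact independence phrase is safe evidence. The powered set is also restricted to patients without recurrence, which may narrow differences in response. The shared acquisitions remain.

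Three stronger readings are tempting and not supported:

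- **That the 85% is an arithmetic error.** It cannot be recomputed from what is readable. The challenge is to a design assumption.
- **That patients already in sinus rhythm would lack the acute gain, which proves unequal response.** Aim 4 does speak of "determining the extent of perfusion improvement acutely due to conversion to sinus rhythm", but the documents give no baseline rhythm, and Inclusion Criteria says research scans are not added at the acute MRI.
- **That Control Group A gives no repeat MPR because its visit-table entry reads "MRI with contrast Blood Draw".** That table is broken in extraction. Procedures puts stress perfusion in the protocol for each study, and the Methods section expects normal MPR values from controls without AF. The point is unsettled.

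**Conclusion.** The independence assumption is unsupported in the readable text and implausible given the shared stress and rest acquisitions. If the territories are combined, any positive correlation leaves 20 patients short of 85% at a valid 5% level. Near zero the shortfall is slight; at moderate correlation a patient-level test has roughly even odds of missing the planned change, and a pooled test has more than three times its nominal error rate. Confidence is high for the direction and medium for the size, which rests on an assumed alpha, a back-solved effect and a correlation range that the documents do not supply. If separate tests were intended, the power figure is unaffected by correlation, but the independence phrase then has no role and should go.

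**What to change.** State the patient as the unit of the primary test: either a paired t-test on each patient's mean MPR change over the three territories, or a mixed model of territory changes with a random patient effect. Remove the word independent from the power statement. Restate the power, or the detectable change, for 20 patients over a stated correlation range (for example 0.2 to 0.8), with the SD of the change and the alpha used. The repeat stress MRIs planned in Control Group B and in the MRI and PET group can inform the measurement-noise part of that SD and correlation, but not the variation in response to ablation.

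The cost is a reworded paragraph and a less favourable stated power. No extra patients or scans are needed if that power is accepted. For scale only, keeping 85% on patient means under the step 1 assumptions would take about 30 / 41 / 53 non-recurring patients at correlation 0.2 / 0.5 / 0.8, against the 20 planned.

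### The primary hypothesis covers ablated patients, but the powered test appears to use only the roughly 20 of 30 who stay free of recurrence, and no all-ablated estimate is planned

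*Combined protocol and SAP*

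**What the plan says.** All of the analysis text is in the section Methods, Data Analysis and Interpretation of the combined protocol and SAP.

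- Hypothesis: "The primary hypothesis is that MPR will significantly increase due to ablation therapy".
- Power, for an MPR change of 0.3: "the power of a paired t-test to detect significant change is 85% with 20" patients.
- Origin of the 20: "30 subjects are planned and it is expected that ~33% of the patients will recur, leaving 20 subjects".
- Patients who recur: "Additional analysis of changes in MPR in the patients that recur will also be done, although with reduced power".
- Recurrence as an outcome: "We will test if MPR is an independent predictor of recurrence".

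Under Purpose and Objectives, aim 4 begins "To determine the changes over time in perfusion reserve and cardiac function and left atrial fibrosis, after ablative treatment for AF". The next sentence gives a reason: "This will allow for determining the extent of perfusion improvement acutely due to conversion to sinus rhythm", together with a slower recovery over months.

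Under Inclusion Criteria, the blood flow cohort is everyone with paroxysmal or persistent AF who is scheduled for catheter ablation. Entry does not depend on later rhythm.

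The available text does not label a primary analysis set. Part of the analysis paragraph is cut off at the margin, but the sentences quoted here can be read.

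**The concern.** The hypothesis is about what ablation does to MPR. The cohort enrolled to test it is every patient scheduled for ablation. The power calculation then removes the patients expected to recur and puts their MPR change into an additional analysis. The natural reading is that the powered paired t-test uses the recurrence-free patients only.

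Recurrence happens after treatment, so this is selection on an outcome. It also differs from ordinary dropout: recurrers remain measurable, and the plan intends to analyse them. The plan treats a link between MPR and recurrence as an open question, since it will test one as a predictor of the other.

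A significant result in about 20 patients would show that MPR rises where ablation held. Read against the hypothesis as worded, it could be taken as the average change after ablation. If recurrers gain less, that average is smaller than the reported figure, and no planned estimate would show by how much.

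**Working it through.** **The plan's own figures.** 30 × (1 − 0.33) = 20.1, so the step from 30 to 20 reproduces. The 85% can be neither confirmed nor refuted, because no standard deviation (SD) of change is readable and the significance level is not stated. Neither is counted as a fault here. For the power and precision figures below I assume a two-sided 5% level and one patient-level SD. Solving the noncentral-t power of a paired t-test for 85% with n = 20 and a change of 0.3 gives SD = 0.425.

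**Subset mean against all-ablated mean.** From the plan: 30 patients, one third recurring, gain 0.3 (applied to those without recurrence). Assumed: recurrers' gain g of 0, 0.15 or 0.3, and the alternative counts of 6 and 14 recurrences.

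All-ablated mean = [(30 − r) × 0.3 + r × g] / 30, with r the number recurring. Excess of the subset mean = 0.3 / (all-ablated mean) − 1.

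For r = 10 and g = 0: (20 × 0.3 + 10 × 0) / 30 = 0.20, and 0.3 / 0.20 − 1 = 50%.

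| Recurring, of 30 | g = 0 | g = 0.15 | g = 0.3 |
|---|---|---|---|
| 6 | 0.24; 25% | 0.27; 11% | 0.30; 0% |
| 10 (the plan) | 0.20; 50% | 0.25; 20% | 0.30; 0% |
| 14 | 0.16; 88% | 0.23; 30% | 0.30; 0% |

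Each cell gives the all-ablated mean, then the excess. These do not depend on the SD. They are not limits: with r = 10 and recurrers falling by 0.15, the all-ablated mean is (6 − 1.5) / 30 = 0.15 and the excess is 100%. If recurrers gained more than 0.3, the subset mean would be too low instead.

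**Precision of an all-ablated estimate.** Half-width of the 95% confidence interval ≈ t × SD / √n.

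- 20 patients: 2.093 × 0.425 / √20 = 0.20.
- 30 patients, g = 0.3: 2.045 × 0.425 / √30 = 0.16.
- 30 patients, g = 0: the difference between the groups adds (2/3)(1/3)(0.3)² = 0.02 to the variance, so SD ≈ √(0.425² + 0.02) = 0.448 and the half-width is 0.17.

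**Power if all 30 were the primary set.** About 96%, 87% and 66% for g = 0.3, 0.15 and 0, against 85% for the 20. Break-even is at g of about 0.13. Working with territories (SD 0.763 back-solved from 60, then 90 in the test) gives 96%, 87% and 68%.

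The 30-patient figures assume that every patient has a usable follow-up scan.

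**The case against.** The strongest reply is that the plan's intent is readable. It derives the 20 by removing recurrers and gives recurrers their own analysis, so the set is clear by implication. It also suits the stated interest in improvement from restored sinus rhythm, a question that patients back in AF cannot answer in the same way. Both points stand, and they are why the recurrence-free set should be kept. They do not bring the hypothesis into line with that set.

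The harm is also partly covered. Recurrers' MPR change will be analysed, and a reader could combine the two subgroup results. That stands too, but the combined estimate and its interval are left to the reader.

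A reader might go further in four ways that the documents do not support.

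- *Recurrers are dropped.* They are not; the plan analyses them separately.
- *The false-positive rate is inflated.* For a zero all-ablated mean with 20 and 10 patients, recurrers would have to fall by twice what the others gain (20d − 10 × 2d = 0). Nothing in the documents suggests this.
- *The 20-patient mean is biased by up to 50%.* No MPR change for recurrers is given, so 50% is one scenario and not a limit.
- *Recurrence was left undefined, so membership of the set could be chosen late.* The text is clipped just after the hypothesis and refers to a section that is not in the available document. A definition may be lost, and at most this would be missing detail.

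**Conclusion.** The point holds in limited form. The powered test appears to condition on a post-treatment outcome, and its conclusion reaches only patients who stay free of recurrence. The hypothesis as worded is wider, and the available text plans no estimate for all ablated patients.

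The consequence depends on a quantity that the documents do not give. At the plan's recurrence rate and with a gain of 0.3 in the others, the subset mean exceeds the all-ablated mean by 50%, 20% or 0% as recurrers gain 0, 0.15 or 0.3. This is illustration only. If recurrers gain as much as the others, nothing is overstated.

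This is a cheap improvement at the low end of severity. It does not show that the planned test is invalid.

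**What to change.** 1. Keep the recurrence-free patients as the set for the powered test, and say so.
2. Word the hypothesis and conclusion to match, for example: MPR increases after ablation in patients who remain free of recurrence.
3. Add a planned estimate of the mean MPR change, with 95% confidence interval, in all ablated patients who have a follow-up scan.

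The cost is a narrower primary conclusion and one extra estimate. The planned power is untouched. No scans are added, because research scans are tied to the ablation date and not to rhythm outcome ("Research scans will not be added in the acute (1-3 days after) MRI studies, but at pre-ablation and at later time points"), and recurrers' changes are already to be analysed. With a usable scan in all 30, the new interval would have a half-width of about 0.16 to 0.17, against about 0.20 for the 20.

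Making all ablated patients the primary set is not part of this fix. It would gain power only if recurrers improve by at least about 0.13 and would otherwise lose it, so it is a trade-off for the sponsor.
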